10.1.2 Study Calendar (Phase II Portion Study)

Baseline clinical evaluations are to be conducted within 2 weeks of starting protocol therapy including a baseline FDG-PET prior to the lead-in phase of imatinib. Radiologic evaluations and surgical biopsies must be done ≤4 weeks prior to the start of therapy. There is a 2-week lead in of imatinib alone and then BGJ398 will be added to imatinib.

Informed Consent can be obtained 30 days prior to study start.

After patients have been on the combination therapy more than 4 cycles, the patient can increase the duration of the evaluation by the MD and RN to every 8 or 12 weeks at the investigator's discretion. The basic laboratory and EKG assessment between evaluations can be performed locally.

Table 11: Visit Evaluation Schedule during Phase II

	Pre-Study	Wk -2	Cycle 1				Cycle 2				Cycle 3 and beyond				Off Study/ EOT ^c
			Wk 1	Wk 2	Wk 3	Wk 4	Wk 5	Wk 6	Wk 7	Wk 8	Wk 9	Wk 10	Wk 11	Wk 12+	
Imatinib ^x		X	X	X	X	X	X	X	X	X	X	X	X	X	

MEMORIAL SLOAN-KETTERING CANCER CENTER
IRB PROTOCOL

IRB#: 14-140 A (7)

BGJ398 ^y																		
Treatment schedule to be determined by the phase Ib portion of the study																		
Informed consent	X																	
Demographics	X																	
Medical history	X																	
Concurrent Meds	X		X	X	X	X	X					X ^d						
Physical exam	X		X	X	X	X	X					X ^d						X
Vital signs	X		X	X	X	X	X					X ^d						X
Height	X																	
Weight	X		X		X		X					X ^d						X
Eye Exam ^k	X						X											
Performance status	X		X	X	X	X	X					X ^d						X
CBC w/diff, plts ^m	X		X	X	X	X	X			X		X ^d						X
Urinalysis	X																	
Blood chemistry ^{a,m}	X		X	X	X	X	X			X		X ^d						X
Hep B	X																	
TSH	X						X					X ^d						
EKG	X				X		X					X ^d						
Echo or MUGA	X						X										X ^e	X
Adverse event evaluation			X		X		X					X ^d						X
Radiologic evaluation	X											X ^f						
Tumor measurements	X											X ^f						X ^f
B-HCG	X ^b																	

MEMORIAL SLOAN-KETTERING CANCER CENTER
 IRB PROTOCOL

IRB#: 14-140 A (7)

FDG PET scan	X				X ^a										
Tumor Biopsy	X			X ^h											X ^h
Research Blood Draw		X ⁱ	X ⁱ		X ⁱ		X ⁱ								X ⁱ
Survival Status															X ⁱ

MEMORIAL SLOAN-KETTERING CANCER CENTER
IRB PROTOCOL

IRB#: 14-140 A (7)


Key for Table 10:
 
Schedule of Phase 2
 
Evaluations
	
X: Imatinib: Dose as assigned; PO once daily
 
Y: BGJ398: Dose as assigned; PO once daily the treatment schedule will be determined by the phase 1b portion of the study
 
a: Comp- Albumin, alkaline phosphatase, total bilirubin, bicarbonate, BUN, calcium, chloride, creatinine, glucose, potassium, total protein, SGOT [AST], SGPT [ALT], sodium. In addition, LDH, phosphorus, magnesium, creatine kinase (CK), amylase, lipase.
 
b: Blood pregnancy test (women of childbearing potential) once at baseline; blood or urine pregnancy test at the discretion of the investigator while on study.
 
c: Off-study evaluation performed 4 weeks after removal from study.
 
d: Day 1 of every cycle while on study. At the investigator's discretion, patients can return for RN/MD visits and get evaluated every 8 or 12 weeks after cycle 4. Laboratory assessments and EKG assessments between MD/RN visits can be performed locally with results sent to the study site
 
e: TTE or MUGA will be performed once at week 16 as well as any time felt to be necessary by the investigator. Modalities should remain consistent whenever feasible.
 
f: Scans should be performed every 8 weeks x 4 starting after 2 cycles (e.g. C3D1, C5D1, C7D1, C9D1), then every 12 weeks (C12D1, C15D1, etc). Radiologic documentation must be provided for patients removed from study for progressive disease within 28 days of clinical assessment of progression if no scan was performed within 28 days of the time of that assessment.
 
g: FDG PET scan will be performed at baseline (pre-treatment) and during week 3 of combination therapy (C1D21).
 
h: Tumor biopsy will be performed pre-treatment, after week 1 (C1D8) of therapy, and at disease progression for patients who have consented for research biopsies including the first twenty mandatory patients and any subsequent voluntary patients. A +/- 4 day window will be provided for the biopsies to account for scheduling.
 
i: Four research blood 4-8mL vials will be obtained at baseline (week -2), two weeks after the single agent imatinib lead in (C1D1 of combination therapy), week 3 (C1D15), week 5 (C2D1). At least one tube at those timepoints will be used for imatinib trough levels, and two tubes will be used for correlative analyses. Imatinib levels will be prioritized.
 
j: Two research blood 4-8mL vials for correlative analyses will be obtained at the time of progression.
 
k: At eye exams the follow tests should be completed : - slit lamp exam - dilated funduscopic exam with photos - optical coherence tomography testing A follow-up eye exam will occur at week 4 (C1W4) and if the patient develops new or worsening ocular symptoms.
 
l: Study personnel will attempt to contact all evaluable patients every 3 months (± 2 weeks) via telephone, email, etc to assess survival status for up to 3 years.
 
m. CBC and Blood Chemistry performed on Day 1 of each cycle must be resulted prior to treatment
 
All assessments are to be done +/-3 days of the scheduled timepoints unless otherwise noted. Radiologic assessments (CT, PET, TTE) are to be done +/-7 days from the scheduled appointment.

--	---

MEMORIAL SLOAN-KETTERING CANCER CENTER
IRB PROTOCOL

IRB#: 14-140 A (7)

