12.1.8 Symptomatic Deterioration

Patients with global deterioration of health status requiring discontinuation of treatment without objective evidence of disease progression at that time will be recorded as “symptomatic deterioration”. Every effort should be made to document objective progression even after discontinuation of treatment.

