12.1.14 Progression-Free Survival (PFS)

PFS is defined as the period from start of study treatment until recurrent or progressive of disease (POD) is objectively documented (taking as reference for progressive disease the smallest measurement recorded on study), death, or date of last contact. For the Phase II portion, start of treatment is defined as the start of the imatinib lead-in period.

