Response rate (RECIST 1.1) will be determined as the proportion of patients evaluable for efficacy (defined as patients who receive at least one dose of the combination regimen) who have complete response or partial response defined by the RECIST 1.1 with a one-sided 90% confidence interval (CI) provided. Patients missing post baseline assessment of response will be considered non-responders for the primary endpoint at that time point.

The steady state serum imatinib trough levels will be obtained and evaluated in the two-week imatinib lead in phase (two samples/patient) and in the combination therapy phase (2 samples/patient) from all patients in the Phase II portion of the trial. We will evaluate the effects of BGJ398 on imatinib steady state trough levels by comparing the values at these two time points (before and after lead in period). We will compare the ranges we obtain with the ranges reported by Demetri et al JCO 2009 and assess whether the effects are considered subtherapeutic, therapeutic, or

MEMORIAL SLOAN-KETTERING CANCER CENTER
IRB PROTOCOL

IRB#: 14-140 A (7)

supra-therapeutic. This analysis may inform future trials with this combination and will not change the dose that will be given in the combination regimen.

The secondary endpoints of the phase 2 portion include:

- (1) RR by CHOI criteria. It will be determined as the proportion of patients evaluable for efficacy who have complete response or partial response defined by the CHOI criteria with a two-sided 95% CI provided.
- (2) RR by EORTC criteria. It will be determined as the proportion of patients evaluable for efficacy who have complete response or partial response defined by the EORTC criteria with a two-sided 95% CI provided.
- (3) Progression free survival and Overall Survival. PFS and OS will be calculated using a Kaplan-Meier estimate among all patients enrolled. They are defined from the start of imatinib treatment, i.e. the lead in period is included in this endpoint. Patients on the Phase II portion who stop study prior to receiving a dose of BGJ398 for reasons unrelated to progression (e.g. intolerance to imatinib) will be censored at the time of withdrawal. Patients who have not had the event of interest by the end of the study will be censored at the time of last follow-up.
- (4) Resectability rate. It will be calculated by the proportion of Phase II patients who have completed 1 cycle of treatment who have resection of their disease with a two-sided 95% CI provided.

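### PFS has no rule for progression called clinically without a confirming scan, and calendar note f can leave such cases undocumented

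*Combined protocol and SAP*

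**What the plan says.** - **Scan rule.** Note f, in the same words for Phase Ib (Table 9) and Phase II (Table 11), requires radiologic documentation for a patient taken off study for progression "within 28 days of clinical assessment of progression if no scan was performed within 28 days of the time of that assessment". Nothing is said about what that scan must show.
- **PFS event.** Section 12.1.14 runs PFS from the start of treatment "until recurrent or progressive of disease (POD) is objectively documented", with death and date of last contact as the other end points.
- **Censoring.** Section 14 (Phase 2 portion): "Patients who have not had the event of interest by the end of the study will be censored at the time of last follow-up". The only special case described is a Phase II patient who stops before the first BGJ398 dose for reasons other than progression.
- **Symptomatic deterioration.** Section 12.1.8 gives a separate label to patients who must stop for declining health without objective progression, and adds: "Every effort should be made to document objective progression even after discontinuation of treatment". Section 14 does not mention this category.
- **After removal.** Section 13 and note l of Table 11 provide for survival status only, every 3 months for up to 3 years.

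**The concern.** Read literally, a patient whose routine scan shows stable disease, and who is judged clinically to have progressed three weeks later and is removed for that reason, already satisfies note f. The PFS definition then finds no objective progression, and Section 14 treats the patient as event-free until last follow-up. If last follow-up is a survival call, the patient gains progression-free time after the investigator had concluded that the disease had progressed.

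The censoring is informative, because the patient leaves on account of presumed progression. The error runs one way, towards longer PFS, and a single-arm trial has no control group in which it would cancel. The documents' own benchmark for imatinib alone is a median PFS of 20 to 24 months (Section 3.1.1).

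**Working it through.** The plan gives no event count, power or target for PFS, so there is no PFS figure to reproduce. The Phase II design figures do reproduce: success at 25 or more of 44, with 45% against 65%, gives an exact one-sided type I error of 0.0775 (stated 0.08) and power of 0.901 (stated type II error 0.1). That rule uses RECIST response and does not depend on this point.

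**1. Inputs**
- Scans every 8 weeks to week 32, then every 12 weeks (note f).
- Window of 28 days (note f); 44 Phase II patients (Section 14).
- True median PFS of 22 months, the middle of the documents' 20 to 24.
- Assumptions not in the documents: exponential PFS, clinical calls spread evenly between scans, and 10%, 20% or 30% of progressions called clinically.

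**2. Share of calls within 28 days after a scan**
- By interval: 28/56 = 50% early, 28/84 = 33% later.
- Over the whole course: monthly hazard = ln 2 / 22 = 0.0315. The chance of progressing in the 28 days (0.92 months) after a scan, if event-free at that scan, is 1 − exp(−0.0315 × 0.92) = 0.0286.
- Event-free probabilities at weeks 8, 16, 24 and 32 are 0.944, 0.891, 0.840 and 0.793, sum 3.47. From week 44 the 12-weekly terms form a geometric series: 0.727 / (1 − 0.917), about 8.73.
- Share = 0.0286 × (3.47 + 8.73) = 0.35. Counting time 0 as a scan would raise it to 38%.
- Section 12.1 allows 6-monthly imaging after a durable response of more than 2 years. If every patient moved to that schedule after week 104, an upper bound on this effect, the share falls to about 27%.

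**3. Effect on the median**

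Let q = (share called clinically) × 0.35. Under the exponential model with censoring at the call, the apparent median is 22 / (1 − q).

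| Called clinically (assumed) | q | Events of 44, if all progress | Apparent median |
|---|---|---|---|
| 10% | 3.5% | 1.5 | 22.8 months |
| 20% | 7.0% | 3.1 | 23.7 months |
| 30% | 10.5% | 4.6 | 24.6 months |

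With 27% in place of 35%, the medians are 22/(1 − 0.027) = 22.6, 22/(1 − 0.054) = 23.3 and 22/(1 − 0.081) = 23.9 months.

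**4. Wider range.** With 5% to 30% called clinically and a window share of 33% to 50%, q runs from 1.7% to 15%. A true median of 20 months then reads 20.3 to 23.5, and one of 24 months reads 24.4 to 28.2.

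**5. Later deaths counted as events.** A simulation kept the lost cases under survival follow-up for up to 36 months and counted death as an event (assumed median survival after progression 24 months; overall follow-up 12 to 60 months). At q = 10%, a true 20 months reads 22.2 under either treatment. A true 24 reads 26.7 with censoring at the call and 26.6 with later deaths counted.

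**6. Yardstick.** With 44 events and a true median of 22 months, the sample median has a 95% sampling range of about 14 to 33 months.

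**The case against.** The strongest reply is that the example patient is already covered. RECIST defines progression in Section 12.1.4. A patient who declines after a stable scan and has to stop is a case of symptomatic deterioration, for whom Section 12.1.8 asks sites to keep trying to document progression. Section 13 has its own removal reason for a change in the patient's condition. Note f can be read as accepting a recent scan only because that scan documents the progression. Its window also covers scans done after the call, where nothing is lost.

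A reader might infer that note f waives documentation outright, that no later scan can recover the case, and that true progressions simply become censored. The documents do not support that. The waiver arises from silence on what the scan must show. Section 12.1.8 points the other way. The off-study columns mark radiologic evaluation (Table 9) and tumor measurements (Table 11), though both marks carry superscript f. Death is a PFS event, so some cases would be late events and not censored ones.

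The size is also open to challenge. The share called clinically is assumed. Visits fall on Day 1 of cycles and may be 8 or 12 weeks apart after cycle 4, so calls can coincide with scans. True progression is also less likely just after a scan without it. PFS is secondary and has no test.

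These points limit the size. They do not close the gap: Section 12.1.8 is a best-effort instruction beside a mandatory rule that contains an exemption, and however hard sites try, Section 14 still has no rule for cases that remain undocumented.

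**Conclusion.** The concern holds as an unhandled case in the PFS analysis, made more likely by the wording of note f. Patients removed for clinical progression or recorded as symptomatic deterioration, without imaging proof, can be censored or counted late and can be credited with progression-free time after the call. The bias is upward.

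Under the stated assumptions, 3.5% to 10.5% of events are lost or delayed, and a 22-month median reads about 22.8 to 24.6 months. The shift is smaller if many patients move to 6-monthly imaging. It rests on an exponential model, even spacing of calls and an undocumented share of clinical calls, and it is small beside the sampling range.

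A reader might infer that the trial's main conclusion is at risk. It is not, since the response rule does not use PFS. A reader might also infer that an extra scan should be mandated or the main PFS event redefined. The first would be a new procedure and a clinical rule. The second would exchange objectivity for completeness. The documents compel neither.

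**What to change.** In Section 14:

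1. Pre-specify a PFS sensitivity analysis that counts removal for progressive disease, or symptomatic deterioration, without radiologic documentation as an event on the date of the clinical assessment. Report it beside the main estimate based on objective progression.
2. State that in the main analysis such patients are censored no later than their last tumor assessment, and not at a later survival contact. Say also whether a later death still counts as their event, since Section 12.1.14 includes death. This removes the credited time after the call but not the informative censoring, which is why the sensitivity analysis is needed as well.

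Separately, reconcile note f (Tables 9 and 11) with Section 12.1.8 on whether a nearby scan that does not show progression satisfies the documentation rule.

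The cost is a few sentences and one more analysis, using removal reasons and dates that Section 13 already requires to be recorded, provided the date of the clinical assessment is captured as well. No additional scan is needed. The drawback is that the sensitivity analysis relies on a less objective event, which is why it should accompany the main estimate and not replace it.

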The phase II portion of the study will be used to confirm the safety and tolerability of the combination and to assess additional efficacy signals of the combination in patients with untreated locally advanced or metastatic GIST. Response Rate (RR) by RECIST 1.1 will be the primary endpoint. Secondary endpoints will include RR by Choi criteria and EORTC criteria for partial response on FDG PET (25% reduction in PET SUVmax) 3 weeks (C1D21) after combination treatment, PFS, OS and resectability rates. Also, the trial will be rich in molecular correlates/exploratory endpoints that will include MAP kinase, FGFR, and KIT signaling pathway inhibition, evaluation of FGF2 and FGFR levels on tumor tissue, FGF2 serum levels, ETV1 inhibition assessed by ETV1 protein levels, and its transcriptional activity based on a custom *ETV1*-dependent gene signature. This combined analysis will be critical to properly design future clinical trials of this combination in patients with locally advanced or metastatic GIST.

The trial phase Ib/II schema is outlined below: (Schema 1):

All participants on the Phase II portion will have a 2-week lead in of imatinib alone. Blood will be drawn at the end of this period to establish steady-state trough imatinib serum levels. After blood for imatinib levels are obtained, BGJ398 at the recommended Phase II dose (RP2D) and schedule will be added to the regimen. The initiation of BGJ398 will not be contingent on the imatinib level; rather,

MEMORIAL SLOAN-KETTERING CANCER CENTER
IRB PROTOCOL

IRB#: 14-140 A (7)

BGJ398 can be started after the blood draws for imatinib levels are performed. The start of the combination therapy will be considered Cycle 1, Day 1.

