5.2.3 Administration of BGJ398

BGJ398 will be taken orally, using treatment schedule A (once a day for 21 days on, 7 days off) or treatment schedule B (once daily for 7 days on, 21 days off) repeating in 28 day cycles. Patients should be instructed to take the daily dose of BGJ398 in the morning, at approximately the same time each day (24 ± 2 hour interval). Patients should consume a light breakfast each day (e.g., non-grapefruit-based juice, toast and jam). This should be followed by a 2 hour fast, after which the doses of study drug should be taken. Patients should continue to fast for 1 hour after the administration of study drug.

BGJ398 should be taken with a large glass of water (~250 mL) and consumed over as short a time as possible. Patients should be instructed to swallow the capsules whole and not chew them. If for any reason a breakfast was not consumed prior to taking the dose the patient should take the dose with a full glass of water, and continue to fast for an hour after taking the dose. If the patient forgets to take the scheduled dose in the morning, he/she should not take the dose more than 2 hours after the usual time and should continue treatment the next day. Any doses that are missed should be skipped altogether and should not be replaced or made up at the next scheduled dosing.

If vomiting occurs following the dosing of study drug, re-dosing is not permitted that same day. Dosing should resume the next day. BGJ398 is characterized by pH-dependent solubility, and therefore, medicinal products that alter the pH of the upper gastro-intestinal tract may alter the solubility of both compounds, and limit bioavailability. These agents include, but are not limited to, proton-pump inhibitors (e.g., omeprazole), H₂-antagonists (e.g., ranitidine) and antacids. Therefore, BGJ398 should be dosed at least 2 hours before or 10 hours after dosing with a gastric protection agent. Patients must avoid consuming Seville oranges or juice, grapefruit, grapefruit juice, grapefruit hybrids, or pummelos from 7 days prior to the first dose of study medication through the end of study participation. This is due to a potential CYP3A4 interaction with study medication. Normal oranges and orange juice are allowed.

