10.2 PATHOLOGY/CORRELATIVE/SPECIAL STUDIES

Tumor Collection and Screening

10.2.1 Pre-treatment diagnosis confirmation:

All patients will have histological or cytological confirmation of a diagnosis at their treating institution prior to treatment. If necessary a patient may have to undergo a biopsy of their disease as per standard clinical practice to ensure that a proper diagnosis of their disease is made. Tissue will be obtained for correlative studies only after a definitive diagnosis has been made by pathology and informed consent has been obtained.

10.2.2 Biopsy specimen collection for correlative studies:

Following informed consent, the first 20 patients enrolled on the phase II portion will undergo mandatory research biopsies. All biopsies will be performed at MSKCC or other participating institutions. These patients will undergo a pre-treatment biopsy and then a post-treatment biopsy (C1D8) that will be performed after week 1 of the combination therapy. Biopsies at the time of progression will be optional but encouraged. After 20 paired biopsy specimens are obtained, the remainder are optional and encouraged if additional funding is identified. If an open incisional biopsy is performed, 1 cm³ of tissue will be flash frozen and 0.5 to 1cm³ will be formalin fixed and sent to pathology for correlative studies. Alternatively, a CT guided core biopsy could be performed. Core biopsy will be performed of a lesion of at least 2 cm by a study interventional radiologist with local anesthesia and through a single entrance site on the skin surface, up to five tissue cores of the GIST will be obtained. Four cores will be flash frozen and one core will be fixed in formalin for correlative pathology. We believe that both approaches will provide sufficient tissue to do the proposed studies. As mentioned in 10.2.1, we may also collect tissue from patients required to undergo a pre-treatment biopsy for confirmation of diagnosis. A patient may be excused from this requirement if tissue is not deemed accessible or for safety reasons as determined by local study investigator. In such a case, subsequent patients will be approached for a mandatory biopsy until a total of 20 paired patient biopsies are obtained. Biopsies will not be performed on the Phase I portion of the protocol.

10.2.3 Research Blood:

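### Phase II sets one biopsy date and one FDG-PET date for two BGJ398 schedules; if Schedule B is chosen, late-window biopsies and every permitted PET day fall after BGJ398 has stopped for the cycle

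*Combined protocol and SAP*

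**What the plan says.** Section 5.2.3 describes two ways of giving BGJ398: "treatment schedule A (once a day for 21 days on, 7 days off") and "treatment schedule B (once daily for 7 days on, 21 days off) repeating in 28 day cycles". Imatinib is taken daily throughout on both. The phase II calendar does not choose between them; the BGJ398 row of Table 11 reads "Treatment schedule to be determined by the phase Ib portion of the study". The clock is defined in Section 1.0: "The start of the combination therapy will be considered Cycle 1, Day 1".

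Two phase II assessments are pinned to that clock, with no variant by schedule:

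- **Biopsy.** Section 10.2.2 calls for a "post-treatment biopsy (C1D8) that will be performed after week 1 of the combination therapy". Table 11 note h adds: "A +/- 4 day window will be provided for the biopsies to account for scheduling".
- **FDG-PET.** Table 11 note g says: "FDG PET scan will be performed at baseline (pre-treatment) and during week 3 of combination therapy (C1D21"). The closing line of the key says: "Radiologic assessments (CT, PET, TTE) are to be done +/-7 days from the scheduled appointment".

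The pre-treatment biopsy (Section 9.0) and the baseline PET (Section 10.1.2) both come before the two-week imatinib lead-in.

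**The concern.** The second biopsy is there to show inhibition of the KIT, FGF and MAPK pathways and of ETV1 under the combination (Section 10.2.5, items 1d to 1f). PET response by EORTC criteria, three weeks into the combination, is a named secondary endpoint (Sections 1.0, 2.0 and 14.0). Both depend on where the patient stands in the BGJ398 dosing cycle, and that differs between the two schedules.

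The protocol's own biology suggests that a few days matter. Section 3.1.3 reports that in GIST cell lines kept on imatinib, p-ERK is switched off and then reactivates around day 3 as FGF signalling comes on, and that BGJ398 shuts it off again. Section 10.2.5, item 1c, describes ETV1 protein as very unstable. A biopsy taken several days after BGJ398 has stopped, with imatinib continuing, may show part of that rebound. The tissue comes from mandatory open or core biopsies and cannot be collected again.

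Phase Ib shows that the issue can be handled. Its pharmacokinetic samples have separate Schedule A and B timepoints, and the Schedule B C1D7 sample has a -2/0 day window that cannot run past the last dose (Section 10.1.1, Tables 9 and 10.B). The phase II biopsy and PET have no equivalent.

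**Working it through.** **1. Inputs.** Dosing days: Schedule A 1-21, Schedule B 1-7 (Section 5.2.3). Biopsy window: 8 - 4 = Day 4 to 8 + 4 = Day 12, 9 days (note h). PET window: 21 - 7 = Day 14 to 21 + 7 = Day 28, 15 days (general rule). Week 3 read literally: Days 15-21, 7 days (note g).

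**2. Day counts.**

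| Assessment | Schedule A: dosing / non-dosing days | Schedule B: dosing / non-dosing days |
|---|---|---|
| Biopsy, Days 4-12 | 9 / 0 | 4 (Days 4-7) / 5 (Days 8-12) |
| PET, Days 14-28 | 8 (Days 14-21) / 7 (Days 22-28) | 0 / 15 |
| PET, week 3 only | 7 / 0 | 0 / 7 |

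**3. Gap since the last Schedule B dose (day minus 7).** Biopsy: Day 8 is 1 day, Days 9-12 are 2-5 days. PET: Day 14 is 7 days, Day 21 is 14, Day 28 is 21.

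**4. Why Day 8 is a trough day.** On Schedule B, Day 8 is about 24 hours after the Day 7 dose. That is the same interval as a pre-dose sample on any dosing day, and it follows a full week of the combination. The days that are off drug in a pharmacological sense are therefore Days 9-12, 4 of 9.

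**5. How much BGJ398 might remain.** The documents give no half-life. Section 3.2.4 gives mean Day 15 to Day 1 AUC ratios of 1.5 to 6.5. Assume linear kinetics and treat the ratio R as the steady-state accumulation factor. The fraction left after each further day is then q = 1 - 1/R, which is 0.333 for R = 1.5 and 0.846 for R = 6.5. Relative to a dosing-day trough, Day D carries q^(D - 8):

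- Day 12: 0.333^4 to 0.846^4, about 1% to 51%.
- Day 14: 0.333^6 to 0.846^6, about 0.1% to 37%.
- Day 21: about 0% to 11%.
- Day 28: about 0% to 4%.

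These are ranges under an assumption. Section 3.2.4 also reports further accumulation beyond Day 15 in most patients dosed without interruption, and active metabolites.

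**6. The plan's own biopsy power.** Section 14.0 states 80% power for 20 pairs at a standardized difference of 0.55, two-sided 10%. The normal approximation gives Φ(0.55 × √20 - 1.645) = Φ(0.815) = 0.79, and n = ((1.645 + 0.842)/0.55)² = 20.4, so the figure is reproduced. The exact noncentral t gives 0.77 at 20 pairs and reaches 80% at 22.

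**7. Illustrative dilution on Schedule B.** Assume biopsies are spread evenly over the nine days, Days 4-8 carry the full effect, and Days 9-12 keep a fraction f of it. The mean effect is 0.55 × (5 + 4f)/9. Exact t power with 20 pairs, ignoring the small extra variance from mixing:

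| f | Mean effect | Power |
|---|---|---|
| 1 | 0.550 | 0.77 |
| 0.75 | 0.489 | 0.68 |
| 0.5 | 0.428 | 0.58 |
| 0.25 | 0.367 | 0.48 |
| 0 | 0.306 | 0.37 |

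If Day 8 is also counted as off drug, the mean effect is 0.55 × (4 + 5f)/9 and the power at f = 0.5 is 0.53. The row f = 0 is an outer bound, because imatinib continues and the comparison is with tissue taken before imatinib.

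**The case against.** Several points on the other side stand.

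- **Schedule B is conditional.** Dosing starts on Schedule A. Schedule B is explored only if dose level 1 to -2 is the MTD, there is concern about activity, and the principal investigator elects it (Sections 4.2, 9.1 and 14.0). It must then be chosen for phase II.
- **A reader might infer that the dates were written for Schedule A.** The documents do not say so. C1D8 also marks the end of Schedule B's dosing week.
- **A reader might infer that most Schedule B biopsies would be off drug and would not measure the combination.** Five of nine days are non-dosing, but one of them is the nominal trough day. The window exists for scheduling, so biopsies will probably cluster near Day 8 rather than spread evenly.
- **A reader might infer that late biopsies are uninformative, or biased toward no change.** Imatinib continues and the baseline precedes it, so KIT and MAPK change need not vanish. What is at risk is mainly the FGF-dependent part.
- **A reader might infer that the Schedule B PET measures imatinib alone.** PET is scored as change from a pre-lead-in baseline and may carry an effect of the BGJ398 week. One week on and three off is the regimen, and the RECIST CT scans on Day 1 of later cycles also follow an off-period on both schedules. Off-drug timing does not by itself invalidate a response measure.
- **The Schedule A count of 7 in 15 holds only if the general window overrides note g.** Read as week 3 alone, it is 0 of 7.

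These points limit the claim but do not remove it. None supplies a Schedule B rule for either assessment. None brings the Schedule B PET near a BGJ398 dose. The two readings of the PET window still need to be reconciled.

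**Conclusion.** The point holds in a limited form, as an inexpensive improvement. The day counts are exact and follow from the text.

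If Schedule B goes into phase II, the biopsy window combines dosing days, a trough day and days 2-5 after the last dose, which can weaken the paired FGF/MAPK/ETV1 analysis. As an illustration, power falls from 0.77 to 0.58 if late samples keep half the effect and biopsies are spread evenly. Both of those are assumptions, and clustering near Day 8 would shrink the loss. The Schedule B PET is 7-21 days after the last dose on every permitted day (14 at the nominal date), so it cannot describe response during concurrent combination treatment, although it may describe response to the regimen.

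On Schedule A the biopsy is unaffected. The PET problem there is the conflict between the week 3 wording and the 7-day window.

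Only a secondary endpoint and exploratory correlates are touched; the RECIST primary endpoint is not.

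**What to change.** 1. **Note h.** On Schedule B, make the biopsy window one-sided: C1D8 with -4/0 days (Days 4-8), no later than about 24 hours after the last BGJ398 dose. Leave Schedule A as it is.
2. **Note g.** Keep the PET inside week 3 with no positive window: C1D21 with -6/0 days (Days 15-21), stated as an exception to the general 7-day rule. On Schedule A this removes all seven off-week days and settles the conflict.
3. **If Schedule B is carried into phase II.** The change to note g still leaves the PET 8-14 days after the last dose. Either reconcile the PET date with the dosing week, or state that the scan is an off-drug, regimen-level response. Moving it to the dosing days of cycle 2 is a debatable trade: it redefines an endpoint that Sections 1.0 and 12.1 place at three weeks and adds imatinib exposure before the scan.
4. **Data and analysis.** Record days since the last BGJ398 dose at every biopsy and PET, and analyse off-drug specimens separately in Section 14.0.

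The cost is tighter scheduling: the Schedule B biopsy window shrinks from 9 days to 5 and the PET window from 15 to 7. There are no extra biopsies or scans and no change to dosing. The wording should be settled before the first phase II biopsy.
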